# 2. Glossary

2WW Two-week wait pathway for cancer diagnosis

PG Progastrin hPG80 Progastrin

CRC Colorectal Cancer
STT Straight to Test
GP General Practitioner

FIT Faecal immunochemical test

GI Gastrointestinal
CRF Case Report Forms
TE Transposable Elements

NBRC National Bowel Research Centre

# 4. Summary and synopsis

	New bioMarkers tO straTlfy cOlorectal caNcer referrals
Short title	(MOTION study)
Methodology	Prospective, observational, cohort study design with post assay result patient questionnaire
Objectives/aims	
 
To determine whether plasma progastrin (PG) levels accurately predict cancer diagnosis in lower GI 2-week wait (2WW) referral patients undergoing standard investigations. The study will also aim to distinguish the absence of cancer by virtue of actual levels of plasma PG.
 
To determine the sensitivity and specificity of plasma PG levels in patients with colorectal cancer (CRC), and benign colonic polyps when investigated via a 2WW referral pathway.
 
To identify and evaluate transposable elements (TEs) in the plasma of patients referred via the lower GI suspected cancer 2WW pathway as potential predictive biomarkers for colorectal cancer diagnosis.
 
To undertake a post-study, patient questionnaire survey exploring the patient preferred characteristics and choices of 2WW CRC diagnostic test(s). Patient experience of a bloodbased test will be explored in detail and compared against other commonly used but more invasive, diagnostic tests using a designed Likert scale questionnaire.
 

Number of participants	Progastrin assay - a total of 582 patients will be enrolled in the study based on an anticipated 18 weeks recruitment period or until the required recruitment number is achieved.  TE assay - 100 (25 proven colorectal cancers and 75 with no cancers) patients from the overall cohort of 582 will be randomly selected for TEs identification and proof of principle validation.
	Inclusion criteria
Inclusion and exclusion criteria	
 
Adult, lower GI 2WW and or Straight to Test (STT) referral patients with suspected lower GI cancer.
 
Male and Female patients aged ≥18 years.
 
2WW referral patients with no history of inflammatory bowel disease.
 
Performance status (ECOG 0-2; and 3 pending clinical assessment of fitness).
 
Patients with capacity to consent to the study.
 
Exclusion criteria
 
Any patients referred outside of the 2WW and or STT referral pathways with suspected Lower GI
 

Officeroity of London	MOTION study
	
 
cancer or those referred as an emergency with or suspected CRC.
 
Age < 18 years.
 
Patients not fit for standard investigations (e.g. not fit for gastroscopy, colonoscopy or CT colonography) in the 2WW pathway.
 
Patients with no capacity to consent or who declined consent for participation.
 
Patients with untreated solid organ cancers.
 
Patients with known inflammatory bowel disease.
 
Patients with documented familial type CRC.
 

Statistical methodology and analysis (if applicable)	The primary outcome will be the accuracy of plasma PG levels to predict a cancer diagnosis in a 2WW referral cohort. Positive and negative predictive values along with the relevant Receiver Operator Characteristic (ROC) curve will be calculated and plotted for patients with confirmed cancer and benign polyp diagnoses.  Secondary outcome of the study is identification and proof of principle validation of novel TEs as potential biomarkers for colorectal cancer diagnosis.
	Tertiary outcome is to explore patient preferences and choices regarding diagnostic test(s) for CRC using an electronic patient questionnaire survey.
Study duration	One year

#### 5. Introduction

At present, the standard practice for investigating bowel symptoms includes a stool based, faecal immunochemical test (FIT) before referral to the 2-week wait (2WW) pathway. The 2WW pathway was introduced into the health system to make a diagnosis of cancer rapidly and set timeline guidelines for the initiation of treatment. The 2WW pathway for colorectal cancer (CRC) in the United Kingdom is designed to ensure that patients referred with suspected cancer symptoms receive rapid assessment and diagnosis. The process typically begins when a general practitioner (GP) or another healthcare professional identifies red flag symptoms in a patient that raise suspicion of CRC. Common symptoms include unexplained weight loss, persistent abdominal pain, changes in bowel habits, and rectal bleeding. The GP then refers the patient to a specialist for further assessment through the rapid assessment 2WW pathway.

The 2WW referral and assessment pathway is bound by strict time guidelines provided by the Department of Health and Social Care. Upon receiving the referral, the specialist service has to complete the first assessment appointment within 2 weeks. All diagnostic tests initiated following the first assessment has to be completed within 6 weeks and patients who were diagnosed with CRC have to commence the first treatment within 31 days of a cancer diagnosis.

#### 5.1. Background

The two-week wait pathway (2WW) is a bespoke pathway aimed at rapidly processing patients with suspected cancer symptoms to enable early diagnosis. There are plans to reduce the timelines stipulated within the current 2WW system which are symptoms based. The criteria for eligibility for a 2WW pathway referral were devised from a set of red flag symptoms circulated to all GPs. Recently the introduction of FIT testing has helped a lot in the process of stratification of patients presenting with red flag symptoms. These new implemented guidelines produce immense pressure on an already over-stretched system and may not be particularly accurate at diagnosing cancers in these sites. A systematic review from 2009 found that when using this symptom profile only 9.5% of patients will have a lower GI cancer.

It would be clinically beneficial to have a diagnostic screening test apart of FIT to predict which symptomatic patients have cancers and which don't. Such a screening test would greatly relieve the target pressure on the health system allowing the most urgent cases to be prioritized and reviewed rapidly. A reliable screening test would also create thresholds for specialist investigations more effectively reducing the overall costs without exposing patients to potential harms from invasive investigations and or a missed cancer.

Progastrin (PG), a circulating blood biomarker, has emerged as a promising tool in the field of cancer detection and monitoring. PG a precursor of gastrin, has been implicated in the pathogenesis of various gastrointestinal diseases, including CRC.

Plasma biomarkers in stratifying patients referred via the lower gastro-intestinal (LGI) suspected cancer two-week wait (2WW) pathway

V5 7th of April 2025

This is because the Wnt / b cadherin pathway coding for b cadherin is abnormal in many GI cancers. A further target of this pathway is the gene encoding PG. PG is converted to gastrin in normal healthy people (and is therefore undetectable) but can be detected in the plasma of many patients with both early and advanced GI malignancy. A study of colorectal polyps and cancers demonstrated an elevated level of PG in cancer subjects compared with benign polyps. Moreover, cancers going on to develop liver metastases produce higher PG levels in plasma. The sensitivity varies between different cancer types but in upper GI and CRCs is 80-95%. This is comparable to "missed" cancers at colonoscopy (3.5%).

Beyond progastrin, transposable elements (TEs), mobile genetic elements that can disrupt gene function, have emerged as promising candidates for cancer biomarker development. Recent research has identified TEs associated with various cancers, including CRC9. However, the role of TEs in predicting CRC diagnosis in 2WW referral cohorts remains underexplored. Liquid biopsy approaches, such as the analysis of circulating free nucleic acids (cfDNA and cfRNA) in conjunction with machine learning algorithms, have shown promise in cancer detection. These methods offer a less invasive alternative to traditional biopsies. Notably, recent studies, including those conducted by the [name] lab, have demonstrated that transposable element-derived RNA signatures can be superior predictors of diseases like pre-eclampsia and cancers. While these findings are encouraging, further research is required to establish the sensitivity and specificity of liquid biopsy approaches for CRC diagnosis. Independent cohort studies encompassing diverse ethnic populations are essential to ensure the generalisability of these methods. Moreover, multi-omics approaches, integrating data from various molecular levels, could enhance the diagnostic accuracy of liquid biopsy assays.

Given that over 90% of patients referred to the lower GI cancer pathway will not have cancer, a screening test or tests to rule out cancers would reduce the burden on NHS targets and could be cost effective at excluding unnecessary tests. The most useful group to be tested and excluded from the pathway in the future would be those patients where the index of suspicion is low. These include those without a family history of CRC, ages between 18 and 55 (not yet eligible for CRC screening programme), no weight loss, good performance status of 0-1 and no history of inflammatory bowel disease.

Global CRC screening programs aim for a 65% participation rate, a target met in many European nations and reaching 74% in the USA. However, CRC screening lags behind breast and cervical cancer screening, which typically exceed 70% participation. A significant barrier to CRC screening is the low attendance rate for colonoscopy or CT colonography following abnormal faecal immunochemical tests (FIT) or faecal occult blood tests (FOBT), ranging from 10% to 30%. This low attendance is often attributed to negative experiences, word-of-mouth discussion, and sociocultural factors.

As emerging technologies like liquid biopsy, utilising biomarkers such as progastrin or transposable elements, offer potential for non-invasive CRC detection, understanding patient preferences for different screening modalities becomes crucial. These tests

vary in invasiveness, frequency, and risk profiles, and their effectiveness in altering risk profiles of CRC differs.

To optimise patient adherence and early detection, it is essential to identify the factors that influence patient choice among these diverse diagnostic options.

#### 5.2. Rationale

For a patient, being placed on the 2WW pathway is stressful and uncertain. Timely and simple diagnostic tools to improve the accuracy and speed of diagnosis will also reduce patients' anxiety. The research hopes to determine whether the addition of a simple blood test to the pathway has the potential to improve diagnosis and patient experience. It also has the potential to deliver cost savings for the overburdened healthcare systems.

Several patients with direct experience of the 2WW pathway developed the research question and design together with the Chief and Co-Investigators. They provided this rationale, co-authored the research proposal, co-designed the study, will serve as members of the project management board, and will fully engage in dissemination and public engagement activities.

#### 5.3. Risks / benefits

The risks of the study involve a single blood draw incorporated in the normal pathway visit. The risks are therefore low: patients may feel slightly faint and will be directed to remain seated for an appropriate amount of time to allow for monitoring.

There are no direct benefits to the study participants involved in this study. However, the knowledge gained from this study may have long term clinical impact on introducing a new blood test in screening suspected lower GI malignancy referrals in the population.

Potential benefits of the study are, principally:

- more effective treatment due to more accurate and timely diagnosis.
- alleviation of patients' stress through more accurate and timely diagnosis.
- shorter time to treatment or discharge.
- avoidance of colonoscopy-related complications by reducing the overall number of colonoscopies used in a 2WW pathway.
- cost savings through avoidance of unnecessary tests.
- non-invasive nature of blood-based biomarkers

# 6. Study objectives

#### 6.1. Primary objective

The primary objective of this study is to test whether plasma PG levels accurately predict the diagnosis of CRC and or polyps in a group of 2WW patients undergoing the standard investigations. The study will also aim to distinguish the absence of cancer by virtue of actual levels of plasma PG. To determine the sensitivity and specificity of plasma PG levels in patients with colorectal cancer (CRC), and benign colonic polyps when investigated via a 2WW referral pathway

#### 6.2. Secondary objective

Identify and evaluate transposable elements (TEs) in the plasma of patients referred via the lower GI suspected cancer 2WW pathway as potential predictive biomarkers for colorectal cancer diagnosis.

#### 6.3. Tertiary objective

To undertake a post-study, patient questionnaire survey exploring the patient preferred characteristics and choices of 2WW CRC diagnostic test(s). Patient experience of a blood-based test will be explored in detail and compared against other commonly used but more invasive, diagnostic tests using a designed Likert scale questionnaire.

#### 6.4. Primary endpoint

The accuracy of plasma PG levels to predict a cancer diagnosis in a 2WW referral cohort. Positive and negative predictive values along with the relevant Receiver Operator Characteristic (ROC) curve will be calculated and plotted for patients with confirmed cancer and benign polyp diagnoses.

# 6.5. Secondary endpoint

Identification and proof of principle validation of novel TEs as potential biomarkers for colorectal cancer diagnosis.

#### 6.6. Tertiary endpoint

Exploration patient preferences and choices regarding diagnostic test(s) for CRC using an electronic patient questionnaire survey.

# 7. Study population

All adult patients who are referred by the GPs to the Barts Health NHS trust under the 2WW referral pathway and the STT pathway would be potentially eligible. We are planning to recruit patients initially only from the Royal London Hospital site and there is potential to expand recruitment to other hospital sites of Barts Health NHS Trust, if necessary. The cancer performance team maintains a running list of all 2WW and STT referrals and these lists will be perused by the study team on a weekly basis to screen for eligible participants. Patients who meet the eligibility criteria (see section 7.1) on initial screening will be sent the study information (PIS) and consent form by post. Further verbal information will be provided during the first clinical appointment (virtual appointment or face to face appointment in the hospital) usually within 1 week of referral and consent to approach sought by the clinical team. The research team will follow-up by contacting patients on their preferred phone number, will answer all relevant questions and will help complete the informed consent form to participate in the study. The study team will re-confirm the informed consent during the subject's normal hospital visit for their 2WW diagnostic test (e.g., colonoscopy, CT Colon) and will draw 20 mL of blood sample for the study. This will occur either in the outpatient department, in the endoscopy department or in the radiology department depending on the reason for and site of their visit. Participants will not be asked to make any additional visits for the study purposes.

Patients will complete the standard diagnostic tests as deemed clinically necessary in the 2WW pathway and decided by the treating clinicians and no change in the standard pathway will be required for participating in the study. The study team will obtain the relevant clinical information and contact details by perusing the patient's electronic health records at the end of the pathway and this information will include the outcomes of the 2WW investigations, particularly the final diagnosis of a cancer, polyp or normal.

Patients will be asked to fill in a post-test questionnaire exploring patient preferences and other quality attributes of potential screening tests after completing their 2WW or STT investigations. The study team will collect this feedback through a e-questionnaire distributed via SurveyMonkey™. The link for the survey will be emailed and texted to the patient's phone number. After 2 weeks a telephone or email remainder will be sent by the research team to those patients who have not completed the questionnaire. A second contact will be made after another 2-5 days, if the questionnaire has still not been returned

#### 7.1. Inclusion criteria

The following inclusion criteria will be used for the study.

- Adult, lower GI 2WW and or Straight to Test (STT) referral patients with suspected lower GI cancer.
- Male and Female patients aged ≥18 years.
- 2WW referral patients with no history of inflammatory bowel disease.
- Performance status (ECOG 0-2; and 3 pending clinical assessment of fitness).
- Patients with capacity to consent to the study.

#### 7.2. Exclusion criteria

The study will use the following exclusion criteria.

- Any patients referred outside of the 2WW and or STT referral pathways with suspected Lower GI cancer or those referred as an emergency with or suspected CRC.
- Age < 18 years.
- Patients not fit for standard investigations (e.g. not fit for gastroscopy, colonoscopy or CT colonography) in the 2WW pathway.
- Patients with no capacity to consent or who declined consent for participation.
- · Patients with untreated solid organ cancers.
- Patients with known inflammatory bowel disease.
- Patients with documented familial type CRC.

Trust approved language line services will be used to aid oral communications for those patients with a lesser command of English and who would need additional support.

# 8. Study design

This will be a prospective, observational, cohort study and will involve all eligible patients who are referred by the GPs to the Barts Health NHS Trust with the suspicion of CRC under the 2WW pathway or STT pathway. This is a single center study where the patients will be recruited from Barts Health NHS Trust, initially only from the Royal London Hospital site. The study will also involve a questionnaire survey at the end of the clinical pathway and will explore patients preferences about screening tests for CRC using a post-test e-questionnaire distributed via SurveyMonkeyTM.

#### 8.1 Progastrin assay

For the PG assay part of the study, approximately 582 consecutive 2WW/STT patients who meet the inclusion criteria will be consented to participate and will have a 'time 0' 20ml of venous blood sample collected. The patients will then undergo the standard clinical investigations that are deemed appropriate by the treating clinicians according to existing hospital protocols. The final (62-day or later for breaches) diagnosis of a colorectal cancer or not will be correlated to the plasma PG levels to determine the predictive usefulness of PG test as a potential biomarker in lower GI, 2WW/STT pathways. The collected blood samples will be processed according to the sample processing protocols.

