#### 10.1. Sample size

Approximate Annual Referral Volume for RLH ≈ 2400 patients per year Recruitment Period:18 weeks (4-5 months)

Eligible Patients:

18 weeks \* (2400 patients/year / 52 weeks ) ≈ 831 eligible patients

Screen Failure:

30% screen failure rate

Potentially 70% of eligible patients enter the study: 831 \* 0.7 ≈ 582 patients

Case and Control Allocation:

Based on cancer office for LGI approximately 9.5% of lower GI patients have a cancer hence:

Cases: 9.5% of 582 ≈ 55 patients with LGI cancer

Controls: (100-9.5)% of 582 ≈ 527 patients without LGI cancer - assuming no other

cancers are detected

Plasma biomarkers in stratifying patients referred via the lower gastro-intestinal (LGI) suspected cancer two-week wait (2WW) pathway

V5 7th of April 2025

Sensitivity and Specificity of PG:

The sensitivity of the PG test is estimated to be between 70% and 87% at a cutoff of 0.2 pM. The specificity of the test at this cutoff is 97.5%.

Statistical Power and Significance Level:

To ensure adequate statistical power, we aim to achieve a power of 0.8 and a significance level of 0.05.

Receiver Operating Characteristic (ROC) Curve Analysis:

A power calculation was performed using the pROC package in R. The following parameters were used:

Number of cases (GI cancer): 55 Number of controls (no cancer): 527 Area under the curve (AUC): 0.6118569

Power = 0.8

To address the secondary outcome of the study a random number of 100 samples out of 582 number of samples (25 LGI cancer proven samples and 75 non-cancer (normal) samples) will be selected and tested for TEs in order to identify and validate novel biomarkers as potential tests for colorectal cancer diagnosis

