#### Primary Outcome Analysis:

Positive and negative predictive values (PPV and NPV) of plasma PG levels in predicting a diagnosis of cancer will be calculated.

Receiver Operating Characteristic (ROC) curve analysis will be conducted to assess the discriminatory ability of plasma PG levels for cancer diagnosis. This includes calculating the area under the ROC curve (AUC).

Sensitivity, specificity, accuracy, and likelihood ratios will also be calculated to evaluate the diagnostic performance of plasma PG levels.

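### The primary endpoint's target condition is named inconsistently (cancer, GI, lower GI, colorectal, CRC and/or polyps), with no rule for a non-colorectal cancer first found on the pathway

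*Protocol*

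**What the plan says.** The protocol describes the condition to be detected in several ways.

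- **Synopsis (4), primary endpoint (6.4), study procedures (9) and primary outcome analysis (10.2):** cancer, with no site. Section 6.4 reads "The accuracy of plasma PG levels to predict a cancer diagnosis in a 2WW referral cohort", and in 10.2 the predictive values concern "plasma PG levels in predicting a diagnosis of cancer will be calculated".
- **Progastrin assay (8.1):** colorectal cancer against everything else. "The final (62-day or later for breaches) diagnosis of a colorectal cancer or not will be correlated to the plasma PG levels"
- **Primary objective (6.1):** "test whether plasma PG levels accurately predict the diagnosis of CRC and or polyps"
- **Statistical considerations (10):** 55 CRC cases and 527 controls.
- **Sample size (10.1):** the same 55 are first patients with lower GI cancer and then, in the ROC power inputs, "Number of cases (GI cancer): 55". The 527 controls are first "patients without LGI cancer - assuming no other" cancers are detected, and then patients with no cancer.

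The 9.5% prevalence behind the 55 also changes label. It is lower GI cancer in 5.1, colorectal cancer in 10, and a cancer in 10.1.

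On progastrin in other tumours, 5.1 states: "The sensitivity varies between different cancer types but in upper GI and CRCs is 80-95" per cent.

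**The concern.** Every participant must go into one cell of the primary 2x2 table. For a patient whose pathway tests reveal a cancer outside the colon and rectum, the protocol does not settle which cell. Under 8.1 that patient does not have the target condition, so a positive progastrin result is a false positive. Under 6.4 and 10.2, read literally, the patient has a cancer diagnosis and the same result is a true positive. If progastrin is negative, the patient moves between true negative and false negative.

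The planning assumption in 10.1 shows that the authors saw the distinction, but it does not say what to do when the assumption fails. The exclusion of untreated solid organ cancers in 7.2 is an entry criterion. It removes cancers already known and is silent on one first diagnosed by the study's own reference tests.

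On the protocol's own account such patients may well be progastrin-positive, at least those with upper GI cancer. With 97.5% specificity only about 13 false positives are expected among 527 controls, so moving a few patients changes PPV, which 6.4 names as part of the primary endpoint. If the choice stays open, it could be made after the progastrin results are known.

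**Working it through.** **1. The plan's own figures reproduce.** Recruitment: 18 × 2400/52 = 830.8, and × 0.7 = 581.5, given as 582. Cases: 9.5% of 582 = 55.3. Controls: 526.7.

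Power uses the Obuchowski variance for a single ROC curve against AUC 0.5, with k = 527/55 = 9.58 and A = 1.414 × z(0.6118569) = 0.4018:

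- V0 = 0.0792(1 + 1/k) = 0.0875
- VA = 0.0099 exp(−A²/2)[(5A² + 8) + (A² + 8)/k] = 0.0882
- z = [√55 × 0.1118569 − 1.96√V0]/√VA = (0.8296 − 0.5797)/0.2970 = 0.841

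This gives two-sided power of 0.7999 against the stated 0.80.

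**2. Inputs for the size of the ambiguity.**

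- From 10.1: 55 colorectal cases, 527 others, specificity 97.5% and sensitivity between 70% and 87%. I take 80%, so 44 true positives and 11 false negatives. Section 10.1 does not say in whom the 97.5% applies; I apply it to cancer-free patients.
- Assumed, because the protocol gives no figure: n = 6 to 17 other cancers (1 to 3% of 582) among the 527, and a share p = 50 to 95% of them progastrin-positive. The 80–95% in 5.1 covers only upper GI cancer and CRC, so the lower end allows for other sites.

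**3. Formulas.** FP = 0.025(527 − n) + pn.

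- Other cancers as controls: specificity = 1 − FP/527; PPV = 44/(44 + FP).
- Other cancers as cases: PPV = (44 + pn)/(44 + FP).
- PPV gap = pn/(44 + FP).
- NPV gap = (1 − p)n/[0.975(527 − n) + (1 − p)n + 11].

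**4. Results.** With no other cancers, FP = 13.2, specificity is 97.5% and PPV is 77.0%.

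| n | p | FP | Specificity (as controls) | PPV (as controls) | PPV (as cases) | PPV gap, points | NPV gap, points |
|---|---|---|---|---|---|---|---|
| 6 | 50% | 16.0 | 97.0% | 73.3% | 78.3% | 5.0 | 0.6 |
| 6 | 80% | 17.8 | 96.6% | 71.2% | 78.9% | 7.8 | 0.2 |
| 6 | 95% | 18.7 | 96.4% | 70.1% | 79.2% | 9.1 | 0.1 |
| 17 | 50% | 21.3 | 96.0% | 67.4% | 80.5% | 13.0 | 1.6 |
| 17 | 80% | 26.4 | 95.0% | 62.5% | 81.9% | 19.3 | 0.7 |
| 17 | 95% | 28.9 | 94.5% | 60.4% | 82.5% | 22.2 | 0.2 |

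Replacing 44 by 38.5 or 47.85 true positives (sensitivity 70% or 87%) moves the PPV gap only to 5.5–24.0 or 4.7–21.0 points.

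**5. Effect of dropping other cancers from the controls.** PPV becomes 44/[44 + 0.025(527 − n)] = 77.2% (n = 6) or 77.5% (n = 17), and specificity returns to 97.5%. Excluding these patients therefore removes the penalty altogether, which bears on the choice of fix.

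**The case against.** The strongest reply is that no section says any cancer. Sections 6.4 and 10.2 leave the site out, in a study of suspected colorectal cancer referrals. Section 8.1, section 10 and the dissemination plan in 20 all point to CRC, so the word could be ordinary shorthand. That has force. A reader might infer that the protocol positively classes an upper GI cancer as a case, but that is only one reading of 6.4. The shorthand explanation still does not account for 10.1, which relabels the same patients twice and needs an explicit assumption to make the labels agree.

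A reader might also infer that gastroscopy is part of the study work-up. Section 7.2 names it only as an example within a fitness exclusion ("not fit for gastroscopy, colonoscopy or CT colonography"). The tests named for participants in sections 7 and 9 are colonoscopy, CT colon and cross-sectional imaging. Imaging alone is enough for another cancer to be found, but the protocol does not say how often that happens.

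The figures above are scenarios, not estimates. PPV is the most sensitive measure shown. Specificity moves little and NPV less, and ruling cancer out is the use that 5.1 stresses. This is a feasibility study with no PPV threshold, and cancer site should be recoverable from the health records. These points lower the severity but do not remove the inconsistency.

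Finally, it is tempting to conclude that the power calculation is wrong. It is not. The label would matter for planning only if the 9.5% included lower GI cancers other than CRC. At an assumed CRC share of 80 to 95% there would be 44 to 52 cases and two-sided power of 0.72 to 0.78, but the protocol gives no such share.

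**Conclusion.** The point holds as an inconsistency in the reference standard of the primary endpoint, with no rule for cancers other than CRC first found on the pathway. It is more than detail left to an analysis plan, because an analysis plan that fixed either reading would sit badly with one section of the protocol.

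Its size depends on assumed inputs. With 6 to 17 other cancers and 50 to 95% positivity, PPV differs between definitions by about 5 to 22 points (about 8 to 19 at 80%). Specificity falls by about 0.5 to 3 points if these patients are controls. NPV differs by less than 1 point in all but one scenario, the exception being 1.6 points at 17 cancers and 50% positivity. If no such cancer occurs, the two readings coincide. Should-fix.

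**What to change.** - Name one primary target, colorectal cancer, as 8.1 and 10 already do. Use it in the synopsis (4) and in 6.1, 6.4, 8.1, 9, 10, 10.1 and 10.2, including the label on the 9.5% and the GI cancer label in the power inputs. Results for polyps can stay as a separately named analysis.
- Record cancer site as a final-diagnosis category, taken from the health records that section 7 already has the team review.
- Keep patients with other cancers in the consecutive cohort and count them as non-CRC in the primary analysis. Removing them by final diagnosis would take out likely positives and raise specificity and PPV, as step 5 of the working shows.
- Pre-specify two secondary 2x2 tables: any cancer as the target, and other cancers excluded.
- Replace the assumption in 10.1 that no other cancers are detected with this rule.

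The cost is protocol wording, one diagnosis code and two small tables. Reported specificity and PPV for CRC may be lower than under the other two definitions, which is why all three should be shown.
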